7.1 Clinical Site Data Management

The Data Coordinating Center will create the electronic data capture (EDC) system that for data entry by clinical site research coordinators and investigators. Data will be entered via the web into the EDC. Worksheets and study documents will be maintained in locked filing cabinets in locked offices at the site.

7.2 Electronic Data Capture System

The Data Coordinating Center currently uses OpenClinica or REDCap as its data capture systems; this may be changed at any time without requiring a protocol amendment.

7.3 Study Monitoring

The investigators recognize the importance of ensuring data of excellent quality. Site monitoring is critical to this process. We will utilize this process to ensure excellent quality data in the proposed study. Our site

monitoring plan is designed to identify problems with sites and methods for handling problems that arise. Site monitors must be provided with full access to study materials and the medical records for study subjects. If the medical records are in electronic form, the clinical investigator or an authorized individual must provide any assistance necessary to facilitate the site monitor's review of data in the electronic medical record.

7.3.1 Site Monitoring Plan

A supplemental study-specific monitoring plan, separate from the protocol will be completed which outlines specific criteria for monitoring. This plan will include the number of planned site visits, criteria for focused visits, or additional visits, a plan for chart review and a follow up plan for non-compliant sites. The monitoring plan also describes the type of monitoring that will take place (e.g. sample of all subjects within a site; key data or all data), the schedule of visits, how they are reported and a time frame to resolve any issues found. Remote site monitoring schedules will be determined by the Data Coordinating Center in coordination with the study principal investigators.

7.3.2 Clinical Site Monitoring

Site monitoring visits will be performed by a trained site monitor during the study period to ensure regulatory compliance, patient safety, and to monitor the quality of data collected. Essential document binders, regulatory documents and data collection forms may be reviewed. Interim visits will take place depending on grant budget, site enrollment, and compliance issues identified. The site monitor will provide each site with a written report, and sites will be required to follow up on any deficiencies. It is anticipated that the study monitoring visits for this protocol will consist of interim visits.

8 Data Coordinating Center

The Data Coordinating Center (DCC) in the Department of Pediatrics at the University of Utah School of Medicine provides data coordination and management services for a variety of national research networks. Anchoring these services is a new state-of-the art, energy efficient data center completed in 2013. The data center facility supports more than 1400 users around the world and provides a secure, reliable, enterprise-wide infrastructure for delivering critical DCC systems and services. The new data center was built using high industry standards and energy efficient cooling solutions. The data center is cooled by Rittal's LCP inline cooling technology, providing efficiency, redundancy and modularity. Cooling is based upon a hot/cold aisle design that allows for even air distribution with minimal hot spots. The data center electrical power system contains a redundant Mitsubishi uninterruptible power system (UPS) with a diesel backup generator. The data center is protected with a FM200 fire suppression system, early warning smoke detectors and a heat detection warning system to act as a secondary system to the smoke detectors. Security guards are on-site conducting access control and rounds. Entry into the data center is restricted by card access and layered security measures and controls. The data center and external building access points are monitored with video surveillance.

- In 2011 the data center began a large scale VMware server virtualization deployment. Currently, the data center has virtualized about 99% of its environment. The virtual environment consists of more than

200 virtual servers. The data center's virtualization solution provides key advantages: high availability – in the event of hardware failure, virtual servers automatically go back online in a seamless process.

- Flexible infrastructure – disk storage, memory and processor capacity can be increased or reallocated at any time.
- Rapid deployment – servers can be provisioned on-demand with minimal waiting on hardware or software.

The data center also enhanced its storage resources by implementing a networked storage system to support its virtualized environment. The data center currently manages over 50 terabytes of data. The storage solution consists of Dell's EqualLogic PS Series Storage system for providing a virtualized storage area network (SAN). Some of the benefits that are realized through this technology are:

- Storage architecture is no longer be a bottleneck for IT services;
- Performance is better than with the previous architecture;
- Tiered storage is now possible;
- Provisioning and reclamation of SAN disk will be much easier; and most important;
- The new architecture includes a redesign of the SAN fabric to include complete redundancy.

Production servers running critical applications are clustered and configured for failover events. Servers are backed up with encryption through a dedicated backup server that connects across an internal 10 gigabit network to a tape drive. DCC storage area networking (SAN) applications, clusters, and switch-to-switch links are also on a 10 gigabit network. Incremental backups occur hourly Monday through Friday from 6 am to 6 pm. Incremental backups also are performed each night with full system backups occurring every Friday. Tapes are stored in a fireproof safe inside the data center facility, and full backups are taken off site on a weekly basis to an off-site commercial storage facility.

In the event of catastrophic failure, such as a fire in the server facility, daily backups would probably survive because of the fire suppression system and fireproof safe, but there would be obvious delay in re-establishing data center function because the servers will not survive such a disaster. Total destruction of the data center facility could cause the loss of up to one week's data. In future investments, the data center is making co-location, disaster recovery and business continuity solutions a top priority.

DCC information systems are available 24 hours a day, 7 days a week to all users unless a scheduled maintenance interruption is required. If this occurs, we notify all users of the relevant systems, and data entry can be deferred until after the interruption is over. Critical systems availability has exceeded 99.9% for the past two years, and there has been no unscheduled downtime in over five years.

8.1 Security and Confidentiality

The data center coordinates the network infrastructure and security with the Health Sciences Campus (HSC) information systems at the University of Utah. This provides us with effective firewall hardware, automatic network intrusion detection, and the expertise of dedicated security experts working at the University. Network

equipment includes four high-speed switches. User authentication is centralized with two Windows 2012 domain servers. Communication over public networks is encrypted with virtual point-to-point sessions using transport layer security (TLS) or virtual private network (VPN) technologies, both of which provide at least 128 bit encryption. All of our Web-based systems use the TLS protocol to transmit data securely over the Internet. Direct access to data center machines is only available while physically located inside our offices, or via a VPN client.

All network traffic is monitored for intrusion attempts, security scans are regularly run against our servers, and our IT staff is notified of intrusion alerts. Security is maintained with Windows 2012 user/group domain-level security. Users are required to change their passwords every 90 days, and workstations time out after 5 minutes of inactivity. All files are protected at group and user levels; database security is handled in a similar manner with group-level access to databases, tables, and views in Microsoft SQL Server. Finally, all laptop computers in use in the DCC or in the Department of Pediatrics are whole-disk encrypted.

The data center uses control center tools to continuously monitor systems and failure alerts. Environmental and network systems are also monitored to ensure up time. Highly trained system administrators on staff are available to respond in high risk emergency events. All personnel involved with the DCC have signed confidentiality agreements concerning data encountered in the course of their daily work. All personnel (including administrative staff) have received Human Subjects Protection and Health Information Portability and Accountability Act (HIPAA) education. We require all users to sign specific agreements concerning security, confidentiality, and use of our information systems, before access is provided.

ITT	Intent-To-Treat
PP	Per-Protocol
(S)AE	(Serious) Adverse Event
SAFETY	Safety Population
SAP	Statistical Analysis Plan

1 PREFACE

1.1 Purpose of SAP

This Statistical Analysis Plan (SAP) describes the planned analysis and reporting for the protocol: A Randomized, Double-Blinded, Placebo-Controlled Study for the Treatment of Ocular Chronic Graft-Versus-Host Disease (GVHD) with processed Amniotic Fluid (pAF) Drops .

This study is a double blind, randomized controlled trial of persons with ocular graph versus host disease. The goal of this pilot study is to collect preliminary data on the safety and efficacy of processed amniotic fluid to reduce pain resulting from dry eye.

The purpose of this SAP is to outline the planned analyses to be completed for the Ocular GVHD trial. The planned analyses identified in this SAP will be included in future study abstracts and manuscripts. Also, exploratory analyses not necessarily identified in this SAP may be performed. Any post hoc, or unplanned, analyses not explicitly identified in this SAP will be clearly identified as such in any published reports from this study.

1.2 Auxiliary/Other Documents

The following documents were reviewed in preparation of this SAP:

- Protocol: A Randomized, Double-Blinded, Placebo-Controlled Study for the Treatment of Ocular Chronic Graft-Versus-Host Disease (GVHD) with processed Amniotic Fluid (pAF) Drops .
- Case Report Forms (CRFs) for the Ocular GVHD protocol

The reader of this SAP is encouraged to read the protocol for details on the conduct of this study, and the operational aspects of clinical assessments.

It is possible that, due to updates or identification of errors in specific statistical software discussed in this SAP, the exact technical specifications for carrying out a given analysis may be modified. This is considered acceptable as long as the original, prespecified statistical analytic approach is completely followed in the revised technical specifications.

2 STUDY OBJECTIVES AND OUTCOMES

2.1 Study Objectives

2.1.1 Primary Objective(s)

The primary objectives of the Ocular GVHD trial are:

1. To determine the safety of pAF in patients with ocular chronic GVHD
2. To determine the clinical effects of pAF in ocular chronic graft versus host disease

2.1.2 Secondary Objective(s)

The secondary objectives of the Ocular GVHD trial are:

1. To determine the change in National Institutes of Health (NIH) Consensus Criteria (CC) ocular score of chronic GVHD at 30 ± 3 days, 60 ± 3 days, and 100 ± 3 days from baseline related to the administration of pAF
2. To determine change in Functional Assessment of Cancer Therapy-General (FACT G) Quality of Life (QOL) at 30 ± 3 days, 60 ± 3 days, and 100 ± 3 days related to the administration of pAF
3. To determine changes in visual acuity related to the administration of pAF
4. To determine the effects of pAF on the corneal surface
5. To determine the changes in dry eye symptoms using the grading provided by the International Dry Eye Workshop (DEWS) 2007 report
6. To determine the changes in patient reported pain level related to the administration of pAF using the 0-10 pain rating scale during the first 60 days of the study

2.2 Study Outcomes

2.2.1 Primary Outcome(s)

The primary outcome is the binary variable of complete or partial response to treatment (as defined by resolution or no worsening on the clinician- reported NIH CC eye score) and a decrease of at least one point on the DEWS.

2.2.2 Secondary Outcomes

The secondary outcomes are

1. Change in the NIH CC ocular score of chronic GVHD
2. Change in FACT G
3. Change in visual acuity
4. To determine the effects of pAF on the corneal surface
5. Change in DEWS
6. Changes in patient reported pain level

3 STUDY DESIGN AND METHODS

3.1 Overall Study Design

This is a randomized, double-blinded, placebo-controlled study of the efficacy of pAF in patients with hematologic malignancies who have undergone Allogeneic Hematopoietic Stem Cell Transplantation (HSCT) and are diagnosed with chronic GVHD of the eye. Patients will be allowed to continue the use of non-medicated lubricant eye drops (artificial tears) for ocular GVHD treatment prior to participating in this study. Patients are allowed to resume the use of eye drops after the 30 day treatment period at the discretion of the treating physician.

Participants will serve as their own control. A person will have one eye randomized to receive pAF and the other eye will receive saline drops.

3.2 Method of Treatment Assignment and Randomization

Upon acceptance into the study, the CTRM facility will be notified and the patient will be randomized as to which eye will receive the drug and which will receive the placebo. Randomization will be done using the MS Excel randomization method as developed by CTRM.

3.2.1 Delivery of Randomization and Emergency Backup

Based on the results of the randomization selection, CTRM will then select appropriate coded boxes. Four boxes containing 8-eyedropper bottles per box will be labeled with a yellow dot and stamped with an R for right eye. Each eyedropper bottle is labeled with a

yellow dot and stamped with an R. Four boxes containing 8-eyedropper bottles per box will be labeled with a blue dot and stamped with an L for left eye. Each eyedropper bottle is labeled with a blue dot and stamped with an L. The boxes will be labeled as Amniotic Fluid Eye Drops, each set (right and left) will contain a total of 32 eyedropper bottles of pAF and 32 eyedropper bottles of placebo.

3.3 Treatment Masking (Blinding)

How are handling treatment assignment in the database? We are going to need to know more than left vs. right. Do we have the treatment labels entered as a form? Why do I have so many questions?

The ocular GVHD study will be performed in a double-blind fashion. All study personnel, including investigators and research coordinators will be blinded as to which eye is receiving the active treatment and which is receiving control.

Of necessity, biostatisticians involved in presenting interim analyses to the DSMB will be aware which subjects have received “Treatment A” and which have received “Treatment B”, but they will not be aware of the identity of the two arms.

3.4 Study Intervention Compliance

Subjects will complete a daily diary indicating their use of the drops in the morning and evening. Participants will note each time there is an issue or the drops are used in a method different than described by the protocol.

4 STUDY SUBJECTS AND ANALYSIS POPULATIONS

4.1 Eligibility

Patients will be eligible for enrollment if they meet all of the following inclusion criteria:

1. Patients with chronic GVHD \geq Grade II diagnosed within 3 years after hematopoietic stem cell transplant (HSCT) for any disease, with any graft, and any conditioning regimen with dry eye (patients may be using bilateral scleral lenses and/or bilateral punctal plugs at the time of accrual)
2. Patients who are 18 years of age or older.
3. Willing and able to provide informed consent.

Patients will be ineligible for enrollment if any of the following exclusion criteria are met:

- Patients who have any other reversible cause for dry eye at the time of accrual.
- More than 2 lines of therapy beyond corticosteroids with or without calcineurin inhibitors or sirolimus
- Relapsed malignancy after transplantation
- A difference in dryness between both eyes of more than 2 points of the grading provided by the International Dry Eye Workshop (DEWS) 2007 report
- Patients who are pregnant or plan to become pregnant while participating in the study.
- Patients who are not willing to discontinue the use of any eye drops, with the exception of non-medicated lubricant eye drops (artificial tears). All eye drops (excluding non-medicated lubricant eye drops) must be stopped at least seven days before treatment with pAF.
- Inability to comply with the investigational plan and visit schedule for any reason, in the judgement of the investigator.

4.2 Populations for Analyses

4.2.1 Screening Population

What do we want? All screened or all eligible? The screening population (SCREEN) includes all patients who are screened for eligibility into the trial, regardless of randomization into the trial or treatment status. This population represents all patients who meet inclusion criteria outlined in the study protocol and who are screened. This population will be used for reporting of study flow per CONSORT guidelines.

4.2.2 Intention-to-Treat Population

The Intention-to-Treat (ITT) population includes all subjects who are randomized into the trial, regardless of adherence to the protocol, including, for example, subjects who receive no study drug. The ITT population will be used for the primary efficacy analyses in the study, as well as for main efficacy analyses of secondary outcomes. All analyses using the ITT population will be based on each subject's assigned treatment arm, regardless of treatment actually received.

4.2.3 Per-Protocol Efficacy Population

The Per-Protocol (PP) efficacy population includes all subjects in the ITT population who are verified to meet all study inclusion and exclusion criteria, who receive study drug according to their assigned study arm and used the drops as specified in the protocol. This population will be used to examine whether results seen in the ITT population are maintained in the population adhering to the protocol.

4.2.4 Safety Population

The safety population (SAFETY) includes all subjects who receive any study drug. Reporting of results based on this population will be summarized according to treatment received. This population will be used for analysis of adverse events and (in addition to ITT) to examine safety outcomes.

5 GENERAL ISSUES FOR STATISTICAL ANALYSES

5.1 Analysis Software

Analysis will be performed using SAS® Software version 9.4 or later whenever possible. Other software packages, including R and StatXact®, may be used for particular specialized procedures.

5.2 Methods for Withdrawals, Missing Data, and Outliers

Per the intention-to-treat principle, subjects who withdraw from the study or are lost to follow-up will have all available data used in the analysis. In the event that a substantial number of subjects are withdrawn or lost to follow-up, baseline characteristics and available information on hospital course will be reviewed and compared to subjects not withdrawn or lost, to assess empirically if these subjects differ from those remaining in the study for the scheduled treatment and follow-up time.

what do we do about participants who miss study visits?

5.3 Multiple Comparisons and Multiplicity

As there is a single primary endpoint for this study, adjustment for multiple comparisons will not be required for the primary analysis.

For the secondary efficacy endpoints, a Bonferroni-Holm stepdown test will be used for assessing significance, with a total alpha level of 0.05 for these two outcomes.

Safety outcomes for this study will be reported using unadjusted p- values for each individual comparison. However, all reports of these outcomes, to the DSMB and in published reports, will explicitly note that multiple safety outcomes have been evaluated. Formal multiplicity-adjusted significance assessments for these outcomes will be performed upon request of the DSMB or other reviewers. The Bonferroni-Holm procedure will be used for such assessments.

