6.3 Secondary Outcome(s) Analyses

6.3.1 NIH Consensus Criteria Ocular Score of Chronic GVHD

The NIH CC will be summarized as above. At each follow-up visit, 30 days, 60 days, and 100 days, the percent of treated eyes that have improved and progresses will be summarized using 95% confidence intervals. To test for a change within participants a sign test will be conducted. An improvement in an eye will be coded as a +1, symptom progression in an eye will be coded as -1, and no change coded as 0. A score will be created for each participant by subtracting the control eye from the treatment eye. Given the sample size it is likely we will use an exact binomial p-value.

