6.3.2 Dry Eye Severity Grading Scheme (DEWS)

The DEWS will be summarized as above. At each follow-up visit, 30 days, 60 days, and 100 days, the percent of treated eyes that have improved and progressed will be summarized using 95% confidence intervals. To test for a change within participants a sign test will be conducted. An improvement in an eye will be coded as a +1, symptom progression in an eye will be coded as -1, and no change coded as 0. A score will be created for each participant

by subtracting the control eye from the treatment eye. Given the sample size it is likely we will use an exact binomial p-value.

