6.3.3 Functional Assessment of Cancer Therapy - General (FACT G)

The FACT-G will be summarized at baseline at the 30, 60, and 90 day follow-up visits using medians and interquartile ranges. The overall FACT-G is calculated by scoring the individual subsections and then deriving an overall score (we need the manual to do this). FACT-G will not be normalized to a 0 - 100 range. A Wilcoxon signed-rank test will be calculated to compare change from baseline at each visit by subtracting the follow-up visit score from the baseline score.

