6.3.4 Visual Acuity

For this outcome it is important to know the percent of subjects with changes, improved or decreased, and the magnitude of the change. To summarize improvement, decrease, or no change at each follow-up visit each eye will be scored as a +1 for an increase in visual acuity, -1 for a decrease in visual acuity, and 0 for no change. Counts and percents will be used to summarize change in visual acuity for both the treatment and control eye. As with the NIH CC and DEWS, the control eye change will be subtracted from the the treatment eye change and a sign test will be conducted.

To estimate a the magnitude of change in acuity, Snellen Chart scores will be converted to LogMAR value. The change in acuity at follow-up for each eye will then be calculated as baseline LogMAR - follow-up LogMAR. The treatment eye change - the control eye change will then be used to conduct a Wilcoxon signed-test.

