6.3.5 Effect of pAF on the Corneal Surface

Changes in the surface of the cornea will be measured using epithelial staining and graded on the following scale: Trace, 1+, 2+, 3+, 4+, Confluent. An improvement at follow-up will be considered to be movement to a lower grade. The treatment and control eyes will be scored at each visit with a +1 for improvement, -1 for decline, and 0 for no change. The number of treatment and control eyes improving and declining at each visit will summarized using 95% confidence intervals. To test for changes within patients the control eye will be subtracted from the treatment eye and a sign test will be conducted.

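### SAP 5.3 sets its secondary Holm correction for two outcomes, but the SAP lists and tests six and never says which two are meant

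*SAP*

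**What the plan says.** SAP 5.3 exempts the single primary endpoint from adjustment. For the secondary efficacy endpoints it then says that "a Bonferroni-Holm stepdown test will be used for assessing significance, with a total alpha level of 0.05 for these two outcomes". Nothing before or after that sentence identifies the two.

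The lists elsewhere have six entries: NIH CC eye score, FACT-G, visual acuity, corneal surface, DEWS and pain. The sixth objective in SAP 2.1.2 is "To determine the changes in patient reported pain level related to the administration of pAF using the 0-10 pain rating scale", and the sixth outcome in SAP 2.2.2 is "Changes in patient reported pain level". Protocol section 2 gives the same six.

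SAP 6.3 attaches a test to every one:

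- **NIH CC (6.3.1):** "To test for a change within participants a sign test will be conducted", with no visit named in that sentence.
- **DEWS (6.3.2):** the same sign test, after a summary described as "At each follow-up visit, 30 days, 60 days, and 100 days, the percent of treated eyes that have improved and progressed".
- **FACT-G (6.3.3):** "A Wilcoxon signed-rank test will be calculated to compare change from baseline at each visit".
- **Visual acuity (6.3.4):** a sign test on direction of change, and then LogMAR differences that "will then be used to conduct a Wilcoxon signed-test".
- **Corneal surface (6.3.5):** "To test for changes within patients the control eye will be subtracted from the treatment eye and a sign test will be conducted".
- **Pain (6.3.6):** one signed-rank test on the difference in slopes.

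Protocol section 6 has no multiplicity rule.

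**The concern.** Holm's procedure is defined by the number of hypotheses in the family. The number stated (two) does not match the number listed and tested (six), and the documents give no way to choose between them. The same secondary result could then be reported as significant or not according to the count the analyst adopts, possibly after seeing the data. SAP 5.6 calls for two statisticians to program the analyses independently, and SAP 5.3 does not give them a single rule to program.

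If the thresholds for two are applied across six outcomes, the total alpha of 0.05 that the SAP claims is not kept. If Holm is run over six with one test each, it is kept.

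**Working it through.** **The plan's own figure.** At step i of Holm with m hypotheses, the threshold is 0.05/(m − i + 1). For m = 2 the steps are 0.025 and 0.05, and 2 × 0.025 = 0.05. The sentence in SAP 5.3 is coherent for a family of two; what fails is the count.

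**Can a family of two be found?**

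- Leaving out FACT-G, which is scored per patient and not per eye, leaves five.
- Protocol section 6 mentions NIH Eye and DEWS together, but without a multiplicity rule or a link to SAP 5.3. It also gives them a signed-rank test where SAP 6.3.1 and 6.3.2 give a sign test.
- Nothing marks any of the six as key or exploratory.

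**Counting individual tests.** Which visits are tested is only partly stated, so two readings are shown.

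- Each visit for everything but pain: NIH CC 3 + DEWS 3 + FACT-G 3 + acuity (3 + 3) + cornea 3 + pain 1 = 19. This is an upper count.
- Each visit for FACT-G only: 1 + 1 + 3 + 2 + 1 + 1 = 9.

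**First Holm step.**

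| Family | Calculation | First threshold |
|---|---|---|
| 2 | 0.05/2 | 0.025 |
| 5 | 0.05/5 | 0.01 |
| 6 | 0.05/6 | 0.0083 |
| 9 | 0.05/9 | 0.0056 |
| 19 | 0.05/19 | 0.0026 |

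A smallest p-value of 0.015 passes only for the family of two.

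**Error rate if all six are judged at 0.025.** The Bonferroni bound is 6 × 0.025 = 0.15; if the tests were independent, 1 − 0.975⁶ = 0.141.

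**Effect on the sign tests.** The SAP does not state sidedness; two-sided is assumed. With n untied pairs, p = 2 × P(X ≥ k), where X is binomial(n, 0.5). The table gives the smallest k that passes the first step, up to the planned maximum of 20 patients (Protocol section 1).

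| Untied pairs | Family of two | Family of six |
|---|---|---|
| 7 | 7 | none |
| 8 | 8 | 8 |
| 9 | 9 | 9 |
| 10 | 9 | 10 |
| 11 | 10 | 11 |
| 12 | 11 | 11 |
| 13 | 11 | 12 |
| 14 | 12 | 13 |
| 15 | 13 | 13 |
| 16 | 13 | 14 |
| 17 | 14 | 15 |
| 18 | 15 | 15 |
| 19 | 15 | 16 |
| 20 | 16 | 17 |

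The cut-offs differ at 9 of 14 counts and agree at 8, 9, 12, 15 and 18. With 6 or fewer untied pairs neither threshold can be reached, since 2 × 0.5⁶ = 0.031. A family of five has the same cut-offs as six throughout. Examples:

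- n = 7: 7 of 7 gives p = 0.0156, which passes for two; nothing can pass for six.
- n = 10: 9 gives p = 0.021; 10 gives p = 0.0020.
- n = 17: 14 gives p = 0.013; 15 gives p = 308/131072 = 0.0023.
- n = 19: 15 gives p = 0.019; 16 gives p = 0.0044.

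**Rough guide to the number of untied pairs.** The SAP gives no assumption for the secondary outcomes. The response rates in SAP section 7, which are for the primary outcome, imply these discordant pairs:

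- 15 patients, 60% v 5%: from 15 × 0.55 = 8.25 to 15 × 0.65 = 9.75.
- 19 patients, 50% v 5%: from 19 × 0.45 = 8.55 to 19 × 0.55 = 10.45.

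In a range of about 8 to 10, two versus six matters at 10 but not at 8 or 9.

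**The case against.** The best defence is that the word two is leftover wording and the rule survives it. SAP 5.3 applies Holm to the secondary efficacy endpoints, SAP 2.2.2 lists six, and Holm over six with one test each does control the error at 0.05. The SAP still contains open drafting questions (for example in 3.3, 4.2.1 and 5.2), so a slip is plausible. That may well be the history, but the text still states a count that contradicts the list. Correcting it also means deciding which visit, and which of the two acuity tests, enters the family.

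Several limits on size stand:

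- Nothing is miscalculated; this is an inconsistency in a decision rule.
- Where both cut-offs can be reached (8 to 20 untied pairs), they differ by at most one patient.
- SAP 5.3 allots alpha to outcomes, not to p-values. In 6.3.1 and 6.3.2 the visit wording governs the percentages, not the sign test. The counts of 9 and 19 are therefore possible readings, with weaker support than two or six.
- The sign-test table covers only the first Holm step, and not the signed-rank tests for FACT-G, LogMAR acuity and pain.
- The discordant-pair range is borrowed from the primary outcome.
- SAP 1.1 describes a pilot study collecting preliminary data.

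These points limit the importance of the defect without removing it. The SAP chose formal alpha control for its secondary outcomes, so the rule has to be one that can be carried out.

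**Conclusion.** The concern holds. The Holm family in SAP 5.3 is inconsistent with the six secondary outcomes listed and tested, and the two it refers to cannot be identified. The first threshold changes threefold between two and six (0.025 v 0.0083), although in patients the difference is usually none or one. This conclusion rests on the text alone; the sign-test figures also assume two-sided exact tests and depend on the number of untied pairs, which the SAP does not predict. Secondary claims are affected. The McNemar test, on which SAP 6.2.1 bases the effectiveness decision, and the sample size are not. It should be corrected, but it does not threaten the trial's main result.

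**What to change.** Before unblinding, replace the reference to two outcomes in SAP 5.3 with a named list of the outcomes in the Holm family, giving one visit and one test for each, and derive the thresholds from that count. Label every other secondary test unadjusted and exploratory. The choice of family belongs to the authors; workable options are:

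- **Five hypotheses, first step 0.01:** the Day 30 between-eye tests for NIH CC, DEWS, visual acuity and corneal staining, plus the pain slope test. FACT-G is reported separately, because each patient receives both products and a patient-level change from baseline cannot compare pAF with saline.
- **All six, first step 0.0083:** one visit and one test fixed for each.
- **Two, first step 0.025:** name the two intended and label the other four exploratory.
- **None:** declare all secondary tests exploratory and remove the 0.05 claim.

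In each case, reconcile the sign test in SAP 6.3.1 and 6.3.2 with the signed-rank test in Protocol section 6 for NIH Eye and DEWS.

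The cost is SAP wording, plus Protocol section 6 if that is where the test is aligned. A family of five or six is stricter than a family of two. Any visit left out has no error control, which matters because Day 60 and Day 100 appear in secondary objectives 1 and 2.
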